4 SELECTION AND ENROLLMENT OF PARTICIPANTS

4.1 Inclusion Criteria

Patients must meet all inclusion criteria to participate in this study:

- Medicare Advantage beneficiary insured by Humana
- Between the ages of 65 and 79
- Having at least two unique fills of any class of hypertension medication within the calendar year
- Adherence level (as measured by the proportion of days covered [PDC] metric) between 60% and 85%

4.2 Exclusion Criteria

Humana policy specifies that certain subgroups of members should not be included in research studies per contractual agreements, privacy policies and rules, or legal requirements. These excluded entities and groups should not be considered part of the overall Humana Research Population. Members that meet the following criteria will be excluded:

- Commercial Fully Insured Groups to be excluded from Research (These are actually employer groups that provide Medicare Group coverage to their retired employees). Each quarter Data Offerings revises and updates the file of excluded Commercial Groups.
 - a. Blue Cross Blue Shield of Florida
 - b. Employees Retirement System of Texas,
 - c. Georgia Department of Community Health
 - d. Ohio Operating Engineers
 - e. Ohio Public Employees Retirement System
 - f. School Board of Broward County
 - g. Public Employees Insurance Agency, an agency of the State of West Virginia,
 - h. Missouri Blind Pension Program
- Florida Medicaid members
- Illinois MMAI members
- Puerto Rico state of residence and from any other geographical areas that are outside of the 50 states (residents of the District of Columbia are not excluded). A few members have residence in the Virgin Islands or other US territories (i.e. Guam, American Samoa). They constitute a small count of patients and cannot be assigned to the 4 geographical areas typically reported for research.
- Administrative Services Only (ASO)
- All Group Medicare members

4.3 Study Enrollment Procedures

For this study, potential participants will be identified through Humana-based datasets. The interventions in this study will be integrated in the usual patient messaging workflow. All Medicare Advantage beneficiaries have provided addresses to Humana

that can be used for mailed communications. 59,997 Medicare Advantage beneficiaries insured by Humana who are not fully adherent to hypertension medications, defined as patients with adherence level (as measured by the Proportion of Days Covered metric [PDC]) between 60% and 85% (i.e., a “refill score” between 60% and 85%).

Study arms include six intervention arms and a usual care arm. All interventions will specifically target hypertension medication adherence. All participants in the six intervention arms will receive two mailed letters. As with other minimal-risk, quality improvement studies the study team has performed that involve the use of routine clinical tools such as patient portals and reminder letters and where informed consent is impracticable, the study team is requesting a waiver of informed consent and HIPAA authorization. There are several reasons for this. One, the nature of this quality improvement intervention involves testing different framing types in patient letters using a similar infrastructure as used during regular insurance communications. Second, the ability to understand the true effect of the intervention as it is delivered in the real world would be difficult to ascertain if formal informed consent from patients were sought. Third, obtaining formal informed consent would predictably reduce the number of patients participating in the study, especially those from under-represented populations, and therefore undermine the generalizability of the study results, a foundational aspect of pragmatic clinical trial principles. In our prior work, the study team has received a waiver of informed consent from the IRB for similar interventions.

5 STUDY INTERVENTIONS

5.1 Interventions, Administration, and Duration

Study arms:

1. A scorecard from Humana reporting patients’ medication adherence using a “refill score”
2. The Arm 1 scorecard plus dynamic social norms messaging (noting the proportion of Humana members improving their medication refill scores)
3. The Arm 1 scorecard, coming from the trusted messenger of a Humana-identified pharmacist taking the same medication
4. A modified scorecard increasing processing fluency through a visual metaphor of “closing the ring”
5. The Arm 4 scorecard plus dynamic social norms messaging
6. The Arm 4 scorecard, coming from the trusted messenger of a Humana-identified pharmacist taking the same medication
7. No mailed message (usual care)

Study participants will be randomized into one of 7 arms. Participants in a treatment arm (arms 1-6 above) will receive 1 of 6 variations of a mailed message informing them of their medication refill score. Participants in the usual care arm will not receive a message. All participants in the six intervention arms will receive two mailed letters in total. The first message will contain the baseline refill score. The second message will be sent within 60 days of the first message and note any changes in the refill score.

5.2 Handling of Study Interventions

Quality control will be completed and messages will be sent by Humana's internal communications teams, who have extensive experience sending similar messages and conducting similar studies. All messages will have similar overall design and language, with the exception of specific sections of the messages that contain the behavioral elements to be tested.

5.3 Concomitant Interventions

None.

5.3.1 Allowed Interventions

None.

5.3.2 Required Interventions

None.

5.3.3 Prohibited Interventions

None.

5.4 Adherence Assessment

Not applicable—no compliance requirements in the study.

6 STUDY PROCEDURES

6.1 Schedule of Evaluations

Assessment	Baseline, Enrollment, Randomization: (Day 0)	Treatment 1 (Day 1)	Treatment 2 (Day 53)	Final analysis
Identification of eligible patients	X			
Enrollment/Randomization	X			
Intervention (control and experimental)		X	X	
Outcome analysis				X

6.2 Description of Evaluations

6.2.1 Screening Evaluation

Consenting Procedure

As with other minimal-risk, quality improvement studies the study team has performed that involve the use of routine clinical tools such as patient portals and reminder letters, formal informed consent will not be sought.

Screening

Eligibility decisions will be decided based on age and adherence level in July 2023.

6.2.2 Enrollment, Baseline, and/or Randomization

Enrollment

59,997 randomly selected study participants will be enrolled from the pool of Humana members who meet all study inclusion criteria and none of the study exclusion criteria.

Baseline Assessments

- Current adherence level as of July 2023.
- Historical, and demographic patient characteristics including age, gender, race, clinical comorbidities and other medication use

Randomization

All study participants will be randomized post-screening and pre-initiation of study intervention.

6.2.3 Follow-up Visits

Not applicable (there are no follow-up visits included in this study).

6.2.4 Completion/Final Evaluation

Not applicable (there are no follow-up visits included in this study).

7 SAFETY ASSESSMENTS

7.1 Specification of Safety Parameters

The study team believes that the risks to participation for members are no more than minimal for several reasons. First, the interventions encourage the refill of hypertension medications indicated for and prescribed by patients' physicians. Second, the study team will not be providing any direct care to patients, and all hypertension medication refill decisions will ultimately be made by the patient, who will have the option of contacting their medical team and/or Humana for advice or specific recommendations. To minimize the risks to privacy from use of patient data, the study team will safeguard any identifiable information and limit access to the information to study investigator actively involved in the research who have all undergone human subjects research training, using a study ID in all other circumstances.

In this pragmatic trial, the study team does not anticipate the occurrence of any incremental adverse events as a result of patients receiving information that encourages them to refill their prescribed hypertension medications on time. All patients involved in the study have been prescribed these medications, and the study team will exclude patients with refill scores that are already $\geq 85\%$. Any adverse events from the medications themselves will be handled in the course of regular clinical care, as they are currently.

7.2 Methods and Timing for Assessing, Recording, and Analyzing Safety Parameters

Not applicable due to the minimal risk profile of the proposed study.

7.3 Adverse Events and Serious Adverse Events

Adverse Event (AE): Any untoward or unfavorable medical occurrence in a human study participant, including any abnormal sign (e.g., abnormal physical exam or laboratory finding), symptom, or disease, temporally associated with the participants' involvement in the research, whether or not considered related to participation in the research.

Serious Adverse Event (SAE): Any adverse event that:

- Results in death
- Is life threatening, or places the participant at immediate risk of death from the event as it occurred
- Requires or prolongs hospitalization
- Causes persistent or significant disability or incapacity
- Results in congenital anomalies or birth defects
- Is another condition which investigators judge to represent significant hazards

Given the minimal risk nature of the study, in which the intervention involves enhanced communication about hypertension medication adherence for Humana Medicare Advantage beneficiaries for quality improvement purposes, the study team does not expect any SAEs or AEs related to the messages delivered in this trial.

7.3.1 Reporting Procedures

No additional SAEs or AEs are expected as expected to take place as a result of participation in this study, as the study team will not be providing any direct care to members and all hypertension medication adherence decisions will ultimately be made by the patient, with the potential consultation of their medical team. If the study team becomes aware of any AEs or SAEs throughout the course of the study, the study team will collect this information.

AE/SAE reporting to the IRB of record will also be completed in compliance with IRB reporting standards.

7.3.2 Follow-up for Adverse Events

No additional SAEs or AEs are expected to take place as a result of participation in this study, as the study team will not be providing any direct care to members and all hypertension medication adherence decisions will ultimately be made by the patient, with the potential consultation of their medical team. However, the study team will be

notified if patients reach out to Humana with feedback about the intervention messages. If the study team becomes aware of any AEs or SAEs throughout the course of the study, the study team will collect and document this information. All AEs will be followed to adequate resolution.

Any medical condition that is present at the time that the participant is screened will be considered as baseline and not reported as an AE. However, if the study participant's condition deteriorates at any time during the study, it will be recorded as an AE.

Changes in the severity of an AE will be documented to allow an assessment of the duration of the event at each level of severity to be performed. AEs characterized as intermittent require documentation of onset and duration of each episode.

Events will be followed for outcome information until resolution or stabilization.

8 INTERVENTION DISCONTINUATION

Not applicable—due to minimal risk of proposed study, there are no discontinuation criteria.

9 STATISTICAL CONSIDERATIONS

9.1 General Design Issues

The study team hypothesizes that messages using dynamic social norms, messenger effects, and processing fluency in combination will more effectively increase adherence compared to usual care, and can identify baseline clinical and demographic characteristics to predict the efficacy of each message.

The primary outcome will be the average end-of-year adherence level in each arm, stratified by refill cycle. The study team will use Humana claims data for outcome measurement, which contains information on prescription claims from pharmacies, as well as patient information. Linear regression will be used to compare outcomes between each intervention arm versus usual care.

9.2 Sample Size and Randomization

The study team estimates a sample size of 59,997 (8,571 per arm) will provide 80% power to observe a ~1% difference in end-of-year adherence level compared to the usual care arm, conservatively assuming a usual care arm rate of 70% and a Holm-Bonferroni corrected alpha of 0.05 to adjust the familywise error rates for multiple hypotheses testing. This difference is significant as the focus of CMS Star ratings measure interventions and are comparable to improvements seen in other similar large-scale behavioral communication studies. In secondary analyses, the study team will compare arms against each other and adjust for any imbalanced baseline characteristics.

9.2.1 Treatment Assignment Procedures

Study participants will be randomized in a 1:1:1:1:1:1:1 ratio with a random number generator into one of 7 arms, stratified by whether participants are on a 30-day

medication refill cycle (~26% of overall study population) or a 90-day medication refill cycle (~74% of overall study population).

9.3 Interim analyses and Stopping Rules

Not applicable—interim analyses are not planned.

9.4 Outcomes

9.4.1 Primary outcome

The primary outcome will be the average end-of-year adherence level in each arm, stratified by refill cycle and adjusting for age, sex, and race.

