Aim 1: Test the effect of dynamic social norms, messenger effects, and processing fluency messages on hypertension medication adherence. The study team will identify 59,997 Medicare Advantage beneficiaries insured by Humana who are not fully adherent to hypertension medications and randomize them to one of six mailed communications to increase medication adherence or control. The primary outcome will be medication adherence (measured by pharmacy refill claims).

Aim 2: Assess association of claims and demographic characteristics with intervention responsiveness. The study team will evaluate the impact of the interventions as a function of baseline levels of adherence, demographic characteristics, and clinical comorbidities to determine the association of patient characteristics with intervention responsiveness. These profiles could be used to target future message content and framing to specific patients most likely to respond.

[figure not shown]
Design and Outcomes

Design: randomized controlled clinical trial of patient-facing messages to test the impact of social norms, messengers, and processing fluency on hypertension medication adherence in individuals 65 to 79 years of age taking medication for hypertension with adherence levels (based on the proportion of days covered metric [PDC]) between 60% and 85%.

The primary outcome will be the average end-of-year PDC in each arm. A secondary outcome will be the proportion of study participants with end-of-year PDC \geq 80%.

See **Figure 1** for an overview of the study design.

Figure 1: Overview of Study Design

Interventions and Duration

Study participants will be randomly assigned to one of seven conditions:

1. A scorecard from Humana reporting patients' medication adherence using a "refill score"
2. The Arm 1 scorecard plus dynamic social norms messaging (noting the proportion of Humana members improving their medication refill scores)
3. The Arm 1 scorecard, coming from the trusted messenger of a Humana-identified pharmacist taking the same medication

4. A modified scorecard increasing processing fluency through a visual metaphor of “closing the ring”
5. The Arm 4 scorecard plus dynamic social norms messaging
6. The Arm 4 scorecard, coming from the trusted messenger of a Humana-identified pharmacist taking the same medication
7. No mailed message (usual care)

Participants will participate in this study for approximately 6 months (through December 2023).

Sample Size and Population

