9.5 Data Analyses

The study team will use Humana claims data for outcome measurement, which contains information on prescription claims from pharmacies, as well as patient information. Regular linear regression will be used to compare outcomes between each intervention arm versus usual care adjusting for the stratified randomized design, age, gender, and race. These adjustments are necessary as the baseline differences in adherence in each of these groups could influence their responses to our intervention.

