10.3.3 Metrics

Quality control metrics for outcome measures will include checks that messages are being a) correctly received based on randomization assignment and b) correctly targeted to 30- vs. 90-day refill cycles. The study team will conduct random checks that targeting is being done correctly.

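### Does the refill-cycle wording leave the primary analysis undecided between six and twelve comparisons?

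*Combined protocol and SAP*

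**What the plan says.** Section 9.1 names as primary outcome the "average end-of-year adherence level in each arm, stratified by refill cycle". Later in the same paragraph it says that linear regression will compare each message arm with usual care. Section 9.4.1 repeats the stratified wording and adds covariates: "in each arm, stratified by refill cycle and adjusting for age, sex, and race".

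Section 9.5, the analysis section, compares "each intervention arm versus usual care adjusting for the stratified randomized design, age, gender, and race". Its next sentence refers to all of these together as adjustments.

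The synopsis (Design and Outcomes) leaves refill cycle out of the definition: "The primary outcome will be the average end-of-year PDC in each arm". The primary hypothesis in 1.1 and section 3 leaves it out too.

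Section 9.2 sizes the trial on whole arms: "8,571 per arm) will provide 80% power to observe a ~1% difference". It invokes a "Holm-Bonferroni corrected alpha of 0.05 to adjust the familywise error rates for multiple hypotheses testing" without listing the tests. It gives a usual care value of 70% but no SD.

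Section 9.2.1 stratifies the randomization by the length of the cycle and gives both shares, with the 30-day group named first: "medication refill cycle (~26% of overall study population) or a 90-day medication refill cycle (~74% of overall study population".

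**The concern.** Section 9.4.1 uses two verbs, stratifying by refill cycle and adjusting for age, sex and race, as if they were two operations. An outcome averaged in each arm and stratified by cycle can be read as one result per arm per cycle: 6 messages x 2 cycles = 12 comparisons. Section 9.5 puts refill cycle with the covariates, which gives six. The Holm family is not listed, so it does not settle the count. The quality check in 10.3.3, that letters are "correctly targeted to 30- vs. 90-day refill cycles", could suggest that the cycles are meant to be looked at separately.

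These comparisons are the trial's main result. If results by cycle were primary, the whole-arm power statement would not describe them, and the 30-day group, about a quarter of the sample, would be poorly powered for a 1-point effect unless the SD is small. If the reading were settled only after the data were seen, familywise error could exceed 5%.

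**Working it through.** **1. Inputs.** From 9.2: 59,997 / 7 = 8,571 per arm, 80% power, a difference of about 1 point, familywise alpha 0.05. From 9.2.1: shares of 26% and 74%, so 0.26 x 8,571 = 2,228 and 0.74 x 8,571 = 6,343 per arm. Two-sided tests and a common SD in both cycles are assumed; the plan states neither.

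**2. The plan's own figure.** Read as proportions (70% versus 71%, 8,571 per arm), power is 30.0% at alpha 0.05 and 11.5% at 0.05/6, so 80% is not reproduced. Read as means, the figure cannot be checked without an SD. Solving 1 = (z_crit + 0.842) x SD x sqrt(2/8,571) gives:

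- alpha 0.05/6: 2.638 + 0.842 = 3.480, so SD = 18.8 points
- alpha 0.05: 1.960 + 0.842 = 2.802, so SD = 23.4 points

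**3. Power by cycle, 12 tests, first Holm step 0.05/12 (z = 2.865).** At SD 18.8 the expected z for 1 point is 3.480 x sqrt(0.26) = 1.774 and 3.480 x sqrt(0.74) = 2.994. Power is Phi(1.774 - 2.865) = 14% and Phi(2.994 - 2.865) = 55%. The result depends on the SD:

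| SD (points) | Pooled, 0.05/6 | 30-day, 0.05/12 | 90-day, 0.05/12 |
|---|---|---|---|
| 9 | about 100% | 80% | about 100% |
| 12 | 99.8% | 47% | 97% |
| 15 | 95.8% | 26% | 81% |
| 18.8 | 80% | 14% | 55% |
| 25 | 49% | 6% | 27% |

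The largest SD that leaves 80% power for 1 point is 18.8 pooled, 9.0 in the 30-day group and 15.2 in the 90-day group.

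**4. Do the two wordings give different estimates?** A stratified comparison in the usual sense weights the cycle-specific differences by stratum size: d = 0.26 x d30 + 0.74 x d90. Randomization is equal across arms within each cycle, so arm and cycle are balanced, and the arm coefficient from a regression with a cycle term equals this same weighted average, apart from rounding in the allocation. Its variance is

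0.26² x 2SD²/(0.26 x 8,571) + 0.74² x 2SD²/(0.74 x 8,571) = (0.26 + 0.74) x 2SD²/8,571 = 2SD²/8,571,

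which is the whole-arm variance used in step 2. A stratified analysis in this sense therefore uses all 8,571 per arm and loses no power.

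**5. Familywise error with no effect in any arm.** By the Bonferroni bound, 6 x 0.05/6 and 12 x 0.05/12 are both at most 5%. A simulation with seven arms, two cycles and a shared usual care arm (2,000,000 runs) gives 4.1% for six pooled tests and 4.2% for 12 tests in one family. A separate six-test family in each cycle gives 8.1%, close to 1 - 0.959² = 8.0%. Choosing between pooled and by-cycle results after seeing the data gives 6.7% to 9.7%.

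**6. The places side by side.**

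| Place | Refill cycle | Comparison |
|---|---|---|
| 1.1 and 3, hypothesis | not mentioned | messages versus usual care |
| Synopsis | only as a randomization stratum | mean per arm |
| 9.1 | stratified by | each arm versus usual care |
| 9.2 | not mentioned | whole arm, 8,571 |
| 9.4.1 | stratified by | mean per arm |
| 9.5 | adjusted for, through the design | each arm versus usual care |

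None of these rows names a test within a cycle.

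**The case for a change.** The strongest case is that a reading which has to be inferred is not prespecified. Section 9.4.1 carries the heading for the primary outcome, and nothing ranks 9.5 above it. The phrase in 9.1 about each arm versus usual care would also suit a regression run inside each cycle. Section 9.5 justifies adjustment by possible differences in response, which is the language of effect modification. The error rates of 6.7% to 9.7% need no SD, and the remedy would be a sentence.

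Part of this stands: the term is not defined and the Holm family is not listed. The rest is weaker. A reading by cycle needs 12 hypotheses that the plan never states. Differences in response belong to Aim 2, whose list of characteristics does not include refill cycle. The check in 10.3.3 concerns mailing and says nothing about the number of primary tests. The inflated error rates require either a choice made after seeing the data or separate Holm families per cycle, and the plan provides for neither. It is fair to say that a claim of 80% power for about 1 point matches the whole-arm size best: at SD 9, pooled 80% power would be reached at 9/18.8 = 0.48 point. But that supports the pooled reading as the intended one; it does not show two competing analyses.

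**Conclusion.** The concern does not call for a change. The wording differs between 9.1 and 9.4.1 on one side and 9.5 on the other, but 9.4.1 reads naturally in agreement with 9.5: one cycle-adjusted contrast with usual care per message, six in all. Following 9.5 as written gives a sound analysis that uses 8,571 per arm and, with Holm over the six contrasts, has familywise error of about 4.1%. Even the 12-test reading in one Holm family would hold it at about 4.2%.

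The 14% and 55% power figures describe an analysis that the plan does not specify, at an SD back-solved from its 80% claim. With an SD of 9 points both cycles would reach 80%. That claim is itself unverified, because no SD is given, so this conclusion does not vouch for it. The conclusion rests on equal allocation within each cycle, which 9.2.1 provides, and on the ordinary meaning of a stratified comparison. The equality of precision in step 4 also assumes a common SD in the two cycles. What remains is a matter of definition that analysts would settle sensibly from 9.5.
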